4.0 Enrollment/Randomization

Patients that fulfill the inclusion criteria and are interested in participating in the protocol will receive detailed instructions about the experimental set-up and

measurements and will be given a consent form. Once deemed eligible, patients will be asked to complete the baseline assessment. After the initial testing is complete, patients will be randomly allocated into one of two groups: low-heat therapy (control) and high-heat therapy. Medical devices and alternative therapies, such as massage and thermal-treatments have shown to be associated with high placebo responses (1). In order to control for this important psychological response, it is imperative to incorporate an appropriate placebo/sham intervention (1). In the present study, we will adopt strategies to minimize the potential confounding effect of psychological and perceptual responses to heat therapy. First, participants will be informed that the purpose of the study is to compare two ‘intensities’ of heat treatment. In the low-heat group, water at 33°C will be circulated through the garment during the treatment sessions. In our initial study (*IRB Protocol #1409063619*) we observed that this strategy evokes a small increase (~0.9°C) in leg skin temperature. In the high-heat group, hot water will be circulated through the garment during the treatment sessions with the goal of increasing skin temperature to 40°C, as observed in our initial study. A random allocation software (Research Randomizer, Social Psychology Network, <http://www.randomizer.org/>) will be used to perform the randomization.

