1	
 1) Medical History and Physical Examination 2) Quality of life assessment 3) Measurement of ankle-brachial index 4) Familiarization with the 6-min walking test 	CTSI's Clinical Research Center at Goodman Hall	2 hrs
2	
 1) Leg MRI (reactive hyperemia) 2) Catheter placement and venous blood draw 3) Measurement of ankle-brachial index 4) Assessment of cutaneous vascular function 5) 6-min walking test 	Imaging Research Facilities and CTSI's Clinical Research Center at Goodman Hall	4 hrs

Table 1: Procedures involved, location and estimated duration of visits 1 and 2.

After the baseline assessment is complete, subjects will be randomly allocated to one of two groups using a random allocation software. Participants will be asked to

attend **3 treatments sessions/week for 6 consecutive weeks**. These sessions will be conducted at the CTSI’s Clinical Research Center at Goodman Hall and will last approximately 110 min. A research coordinator will supervise the patients during the sessions. On each session, subjects will initially have their body weight and blood pressure measured and recorded. Next, patients will be asked to change into the water-circulating pants (Figure 3) and lay in semi-recumbent position. The garments will be connected to the water pump and the treatment will be applied for 90 min. In the high-heat group, hot water will be circulated through the garment with the goal of increasing skin temperature to 40°C, while thermoneutral water (33°C) will be used in the low-heat group. Subjects will be allowed to drink water ad libitum during the sessions but will not be allowed to consume food. At the end of the session, body weight and blood pressure will once again be recorded. The research coordinator will measure temperature (sublingual measurements) and blood pressure every 15 minutes during the treatment and will also inspect the skin in the legs to look for potential signs of injury or adverse reactions to the treatment. The subject will be asked to complete a heat sensation scale every 15 minutes during the treatment. The research coordinator will clean the garment after each use using a hospital-grade disinfectant spray. The garment will also be washed in a washing machine every week.

Figure 3: Water-circulating garment system for thermotherapy application

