Leg heating: Hot water (47-50°C) will be perfused through the water-circulating garment with goal to increase skin temperature in the calf to 40°C. It is possible that the tubes in contact with the skin could cause discomfort due to a sensation of warmth/heat. Should the tubing that is in contact with the skin cause discomfort we will readjust the suit or turn down the temperature of the water. Ninety minutes of heating will likely lead to skin redness and flushing, which are typical responses to local heating. These effects are temporary and will fade once the heating stimulus is terminated. Once instance of skin being burned to the point of blistering has occurred. The research coordinator will examine the patient's skin during each treatment session for potential signs of injury or adverse reactions to the treatment.

A sophisticated, research-grade heated bath circulator will be used to circulate water through the garment. The actual device we use (SC100) and its technical specifications are displayed in the document entitled "SAHARA S21 Stainless-Steel Heated Bath Circulators." The temperature stability of this heated bath circulator is 0.02°C. This is a remarkably small variation, which supports the notion that there are no risks of sudden oscillations water temperature.

The actual temporal behavior of skin temperature during 90-minutes of thermotherapy application is shown on the figure on page 4 of the protocol. There are no abrupt changes in temperature. The response follows an exponential rise to a peak of around 39.5°C at 90 minutes. This temperature is safe and far below the temperature required to burn the skin, which is typically above 43°C.

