Our initial study revealed that the proposed protocol leads to a progressive increase in leg skin temperature from a baseline of 33°C to ~39.5°C. A research coordinator will supervise each treatment session. If the patient experiences any discomfort or burning sensations, the coordinator will readjust the suit or turn down the temperature of the water. Subjects will be reminded to remain in a semi-recumbent position during treatment and will also be asked to rate heat sensation every 15 minutes using a thermal sensation scale to monitor for excessive heat levels on the skin. If subject reports a grade of 3 ("Hot") or above, or any discomfort, the coordinator will readjust the suit and turn down the temperature of the water. If, after reducing the temperature and readjusting the suit the patient again reports a grade of 3, we will keep repeating the aforementioned steps until the score drops down and the patient feels comfortable. Water temperature

will be assessed and recorded every 15 minutes using the temperature display on the pump.

In preliminary experiments we observed that thermotherapy application induces a minor reduction in blood pressure in some patients. The research coordinator will measure blood pressure prior to and every 15 minutes throughout the application. If the patients experience dizziness, lightheadedness or any other symptom of hypotension, the therapy will be terminated and the participant will be placed supine with the legs elevated. Blood pressure will be checked every 5 minutes until the symptoms disappear and blood pressure returns to baseline levels.

Venous blood sampling: During catheter insertion there is a risk of pain from the needle. Bleeding, local swelling, bruising and formation of a hematoma might also occur around puncture site. By using appropriate phlebotomy techniques, the risks associated with catheter placement and repeated sampling are minimized.

Blood pressure measurements: There are no risks associated with the blood pressure measurements.

Measurement of calf muscle oxygenation: There are no risks associated with blood pressure measurements.

MRI scan: Potential risks associated with MR imaging include:

- Claustrophobia: the confining conditions of the MR scanner can cause claustrophobia. If the patient experiences claustrophobia the scan will be stopped.

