8.0 Statistical Considerations

Sample size was estimated based on the ability to detect a significant change in 6-min walk distance from baseline to 6 weeks in the TT-treated group as compared to the control group. The studies of McDermott and co-workers (5) and Gardner and co-workers (2), which investigated the impact of home-based exercise training on walking tolerance in patients with IC, were used as a reference for the sample size calculations. We estimated the variance of improved walk distance by the MSE of Table 3 in the study of Gardner et al (2), which is 48.69 meters. Since both studies reported a non-significant change in 6-min walk in the attention-control group (95% confidence interval for McDermott's study is (-25.4 to 3.2) and for Gardner's study is (-6.33 to 14.33)), we predict that the change in 6-min walk in the control group, in our study, will be negligible (0). As pointed out by Perera et al (6), a change of 50 meters in the 6-min walk test is considered substantial and clinically meaningful in elderly subjects. Using this effect size $(50-0)/48.69$, we determined that **16 subjects per group** are needed to detect a substantial improvement by TT therapy with a power of 0.802.

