Leg thermotherapy for intermittent claudication

NCT02770547

Document Version: 12/11/2019

Statistical Analysis Plan

Demographic and clinical characteristics were summarized overall and by group. Two-sample tests, Wilcoxon Rank Sum test, Chi-square tests, or Fisher's Exact tests were used to compare the two groups. For the analysis of MRI-derived indices, absolute values were used for peak flow and flow per minute as sometimes the values reported from the machine were negative. Percentage change in peak flow is defined as $(\text{max absolute value} - \text{mean baseline absolute value}) / \text{mean baseline absolute value}$. For the outcome of 6-min walk test, the best of V1 and V2 was used as baseline. For the MRI-derived indices, the blood parameters, cutaneous microvascular function, and the experimental blood pressure, V2 was used as the baseline; while for the quality of life, V1 was used as the baseline. For physiological variables of systolic blood pressure, diastolic blood pressure, mean arterial pressure, heart rate, and temperature in the ear, change from baseline at each time point using the mean of total 18 sessions in two groups was plotted. Area under the curve (AUC), expressed as arbitrary units, for the total 90 minutes was plotted. The AUC for the change from baseline was also plotted in each session in each group. For the cutaneous microvascular function, mean arterial pressure, cutaneous vascular conductance (CVC) and MaxCVC were plotted by mean with standard error at each time point in each experimental visit; AUC for the total 14 time points were also plotted. In the experimental blood pressure, means with standard error were plotted for the change of systolic blood pressure, diastolic blood pressure and mean arterial pressure from baseline timepoint in high-heat therapy group or low-heat therapy group separately; change of AUC in systolic blood pressure, diastolic blood pressure and mean arterial pressure from baseline visit V2 were also plotted. For 6-min walk test, MRI-derived indices, blood parameters, quality of life, the AUC of cutaneous microvascular function indices, and AUC of experimental blood pressure, analyses were done with two different model types. First, linear mixed models with fixed effects for visiting time (V1 or V2, V3, V4) and intervention (high heat, low heat) were fit using the raw data. A significant interaction of time and intervention would indicate that there were differential effects of high and low heat over time. If the interaction was not significant, it was removed. In the main effects only model, a significant main effect for intervention would indicate that the two intervention groups are different (with the same magnitude of difference) across all time points (including baseline). Second, the changes from baseline to V3 and baseline to V4 were modeled with a linear mixed model. Here a significant interaction of time and intervention would mean the intervention effect was different at V3 vs V4. If the interaction was not significant, it was removed. In the main effects only model for change, a significant main effect for intervention would mean that there was an intervention effect, and it was of the same magnitude at V3 and V4. As the results were largely consistent, the results section focuses on the change score model results. Two sample t-tests were used to check whether the AUC for the change of physiological variables were different between two treatment groups. For the cutaneous microvascular function, the MaxCVC from two laser Doppler probes were compared at each timepoint using the linear mixed model with fixed effects for time point and probe, a significant interaction of timepoint and probe would indicate that the MaxCVC from two probes are different over time. The probe effects at each time point were also tested when the probe by time interaction was statistically significant at the significance level 0.05, or the main effects of probe were checked if the probe by time interaction was not statistically significant at the significance level 0.05. All analyses were performed using SAS v9.4.

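### Does turning the water down for comfort leave the heat delivered so poorly documented that the plan must change?

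*Protocol*

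**What the plan says.** Protocol sections 4.0 and 5.0 define the high-heat treatment by a goal. The leg-heating text in section 5.0 has water at 47–50°C circulated "with goal to increase skin temperature in the calf to 40°C". The low-heat group receives water at 33°C.

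The same text makes delivery depend on tolerance. At a heat-sensation grade of 3 or above, or any discomfort, the coordinator adjusts the suit and lowers the water temperature. If grade 3 is reported again, "we will keep repeating the aforementioned steps until the score drops down and the patient feels comfortable". No lower limit is stated.

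On session measurements, section 5.0 says: "The research coordinator will measure temperature (sublingual measurements) and blood pressure every 15 minutes during the treatment". It adds body weight, skin inspection and a heat-sensation score. Water temperature "will be assessed and recorded every 15 minutes using the temperature display on the pump". Skin temperature is not in the list. The expected skin response, "a progressive increase in leg skin temperature from a baseline of 33°C to ~39.5°C", comes from the investigators' preceding single-session study.

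The SAP's session variables are introduced thus: "For physiological variables of systolic blood pressure, diastolic blood pressure, mean arterial pressure, heart rate, and temperature in the ear". Their change from baseline is plotted over time. Areas under the curve (AUC) are plotted by session and group and compared between groups by t-test. Water temperature and heat-sensation scores are not mentioned.

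**The concern.** A treatment defined by a target but delivered to tolerance can differ between patients and sessions. If many high-heat patients had the water lowered, the contrast between arms would shrink. A small difference in 6-minute walk distance could then mean either that heat at the goal does not help or that the goal was not reached. A positive result would also lack a full description of the heat behind it.

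The gap seems careless because water temperature is recorded throughout each session and then absent from the SAP. The sample size leaves little slack, so a modest loss of effect would matter.

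**Working it through.** **1. The plan's own power.** Inputs from Protocol section 8.0: difference 50 m, SD 48.69 m, 16 per group. No alpha is stated; two-sided 0.05 is assumed.

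- Standard error = 48.69 × √(2/16) = 17.21 m.
- Noncentrality = 50 / 17.21 = 2.90, with 30 degrees of freedom.
- Power from the noncentral t distribution = 0.8025, which matches the stated 0.802.

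**2. What a shortfall might do, as illustration only.** For the low-heat water, section 4.0 reports: "we observed that this strategy evokes a small increase (~0.9°C) in leg skin temperature". The skin contrast between arms in the preceding study was therefore about (39.5 − 33) − 0.9 = 5.6°C. It would be 7.0°C if the rise of about 7°C in section 2.0 is already relative to control. Assume effect = 50 × (contrast − shortfall) / contrast.

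| Mean shortfall | Effect at 5.6°C contrast | Power at 5.6°C | Power at 7.0°C |
|---|---|---|---|
| 0°C | 50.0 m | 0.80 | 0.80 |
| 0.5°C | 45.5 m | 0.73 | 0.74 |
| 1°C | 41.1 m | 0.64 | 0.67 |
| 2°C | 32.1 m | 0.44 | 0.52 |

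The arithmetic is sound but its premises are not in the documents. Section 8.0 justifies 50 m because "a change of 50 meters in the 6-min walk test is considered substantial and clinically meaningful in elderly subjects". That is a threshold of clinical relevance, not the benefit expected at 40°C. Neither document gives a dose-response, a turn-down frequency or a shortfall. It is also unknown whether comfort adjustments had already been made in the study that gave 39.5°C, so zero shortfall is not an established reference.

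**3. What the unused readings could show.** At full attendance there are 90/15 = 6 readings per session, 6 × 18 = 108 per participant, and 108 × 16 = 1,728 in the high-heat group. They are readings from the pump. With water at 47–50°C and a skin goal of 40°C, the intended gap between water and skin is itself 7–10°C. Readjusting the suit can change heat at the skin without changing the display. Neither document says that turn-downs are logged as events, so they could only be inferred from successive readings. The table would describe the water, not attainment of the skin goal.

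**4. What the SAP already provides.** Section 2.0 gives the acute response in the preceding study relative to control: systolic pressure down about 12 mmHg, diastolic down about 6 mmHg, core temperature up about 0.6°C. The SAP analyses session blood pressure and a body temperature by group, so a reader can judge whether high heat produced its expected systemic response. (The protocol takes that temperature under the tongue and the SAP in the ear. The two should be reconciled when results are reported; the point here does not depend on it.)

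**5. The wording on discomfort.** One sentence has the suit readjusted or the water lowered; a later one has both done. Doing both satisfies each, so this is loose wording rather than a contradiction. Aligning it is for the clinical team.

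**The case for a change.** The strongest case for a change is that the SAP's markers are systemic. A core rise of about 0.6°C against about 7°C at the leg skin is a weak guide to local heat, and blood pressure cannot show how far the water was lowered. The readings should already exist, a table is cheap, and it could be labelled post hoc and kept descriptive.

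Much of this stands. The indirect markers do not verify 40°C at the skin, and a summary of water temperature and heat-sensation scores would help a reader describe the treatment. But the table does not resolve the ambiguity either, for the reasons in step 3. Nor could it support an adjusted or subgroup analysis: heat tolerated arises after randomisation, and selecting on it would lose the protection of random allocation. The SAP is written in the past tense and refers to results, so a skin measurement cannot now be added to sessions already held.

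**Conclusion.** No change to the plan is needed. The omission is real but narrow: recorded water temperatures and heat-sensation scores are not summarised, and no session skin temperature is listed. It is too strong to say that delivered heat goes unreported, because its systemic effects are plotted by session and group and tested.

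The as-randomised comparison answers a sensible question: the effect of aiming for high heat, adjusted to comfort, against low heat. A descriptive table would change no estimate, test or sample size. The power losses in step 2 depend on an assumed proportional dose-response and an assumed shortfall, and should not be quoted as the size of the problem.

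Analysts can sensibly fill the gap when reporting, by describing the pump readings and sensation scores post hoc and saying whether skin temperature was recorded. That is optional. This conclusion assumes that the primary comparison stays as randomised and that no claim is made that 40°C at the skin was verified in these sessions.

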7.0 Study Withdrawal/Discontinuation

Participation in this study is voluntary. Participants may choose not to participate or, if they agree to participate, they can withdraw their participation at any time without penalty or loss of benefits to which they are otherwise entitled.

8.0 Statistical Considerations

Sample size was estimated based on the ability to detect a significant change in 6-min walk distance from baseline to 6 weeks in the TT-treated group as compared to the control group. The studies of McDermott and co-workers (5) and Gardner and co-workers (2), which investigated the impact of home-based exercise training on walking tolerance in patients with IC, were used as a reference for the sample size calculations. We estimated the variance of improved walk distance by the MSE of Table 3 in the study of Gardner et al (2), which is 48.69 meters. Since both studies reported a non-significant change in 6-min walk in the attention-control group (95% confidence interval for McDermott's study is (-25.4 to 3.2) and for Gardner's study is (-6.33 to 14.33)), we predict that the change in 6-min walk in the control group, in our study, will be negligible (0). As pointed out by Perera et al (6), a change of 50 meters in the 6-min walk test is considered substantial and clinically meaningful in elderly subjects. Using this effect size $(50-0)/48.69$, we determined that **16 subjects per group** are needed to detect a substantial improvement by TT therapy with a power of 0.802.

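### The stated power of 0.802 needs 16 week-6 walk results in each arm; the protocol makes no allowance for loss, and one missing result takes the planned comparison below 0.80

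*Protocol*

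**What the plan says.** Protocol section 8.0 sizes the trial on the "change in 6-min walk distance from baseline to 6 weeks in the TT-treated group as compared to the control group". The target rests on a cited statement that "a change of 50 meters in the 6-min walk test is considered substantial and clinically meaningful in elderly subjects", with no change expected in the control arm. The spread is taken from a published home-exercise trial, "which is 48.69 meters". From these inputs, "16 subjects per group" "are needed to detect a substantial improvement by TT therapy with a power of 0.802".

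The section gives no attrition rate, no inflated number and no distinction between enrolled and evaluable patients. Section 4.0 (Enrollment/Randomization) gives no recruitment number.

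After allocation, section 5.0 asks for "3 treatments sessions/week for 6 consecutive weeks". That is 3 × 6 = 18 supervised clinic sessions of about 110 minutes each. Outcome visits of about 4.5 hours follow at 3 weeks (V3) and at the end of treatment (V4). Section 7.0 says of participants that "they can withdraw their participation at any time without penalty".

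The SAP gives no sample-size update and no rule for missing data. It takes the better of the V1 and V2 walks as baseline. It then models the V3 and V4 changes in a linear mixed model with time and intervention, dropping their interaction if it is not significant. It names no baseline covariate in that model.

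**The concern.** A power of 0.802 leaves almost no margin over 0.80, so the figure depends on nearly every allocated patient giving a week-6 walk test. Some loss is foreseeable from the protocol itself. The schedule is demanding, withdrawal is free, and section 1.0 names frequent clinic visits as the obstacle to supervised exercise for most of these patients. Assuming no loss therefore needs a justification, and none is given.

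What is at stake is how a non-significant walk result is read. A reader who takes 0.802 at face value would put the chance of missing a true 50 m difference at about 20%. With 14 or 13 results per arm, the chance under the same assumptions is about 26% or 29%.

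**Working it through.** **Inputs.** From protocol section 8.0: difference 50 − 0 = 50 m; SD 48.69 m; 16 per arm. The text calls 48.69 a variance taken from an MSE, but gives it in metres and divides 50 by it, so it is used as an SD. Assumed: two-sided alpha of 0.05. Section 8.0 states no alpha, and the SAP gives 0.05 only for the comparison of the two laser Doppler probes.

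**Formula.** Two-sample t-test with n₁ and n₂ results:

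- standardised effect d = 50/48.69 = 1.027
- noncentrality λ = d / √(1/n₁ + 1/n₂)
- degrees of freedom = n₁ + n₂ − 2
- power = probability that a noncentral t with noncentrality λ lies beyond ± the 97.5% point of t

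**Reproducing the stated figure.** At 16 per arm, λ = 1.027/0.3536 = 2.905 on 30 df with critical value 2.042, so power = 0.8025. This matches 0.802. At the same n, the two-sided normal approximation gives 0.828, the one-sided t-test 0.884 and the one-sided normal 0.896. Of the variants tried, only the two-sided 0.05 t-test fits, which is why that alpha is inferred.

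**With fewer week-6 results:**

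| Results per arm | λ | df | Power | Difference detectable at the stated power |
|---|---|---|---|---|
| 16 and 16 | 2.905 | 30 | 0.802 | 50 m |
| 16 and 15 | 2.857 | 29 | 0.789 | – |
| 15 and 15 | 2.812 | 28 | 0.775 | 51.8 m |
| 14 and 14 (12.5% loss) | 2.717 | 26 | 0.744 | 53.7 m |
| 13 and 13 (19% loss) | 2.618 | 24 | 0.710 | 55.9 m |

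**What the V3 data could add.** Suppose that the V3 and V4 effects are both 50 m, that both changes have SD 48.69 m, that they correlate at ρ, and that each remaining patient has both visits. The mean of the two changes then has SD 48.69 × √((1 + ρ)/2). The documents do not give ρ, so a range is shown:

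| Per arm | ρ = 0.7 | ρ = 0.8 | ρ = 0.9 |
|---|---|---|---|
| 15 | 0.84 | 0.82 | 0.795 |
| 14 | 0.81 | 0.79 | 0.77 |

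A smaller effect at V3 than at V4 would reduce these figures.

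**What a baseline covariate could add.** If baseline and change correlate at r, the residual SD is 48.69 × √(1 − r²). Putting this into the power formula, and charging one degree of freedom, the stated power returns at 14 per arm if |r| is about 0.37 and at 13 per arm if |r| is about 0.45. The documents do not give r. The formula also assumes that 48.69 m is not already adjusted for baseline, which cannot be checked because the cited table is not in the documents.

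**The case against.** The strongest reply is that the SAP does not plan a t-test at V4 alone. Its mixed model pools the V3 and V4 changes when the interaction is dropped, so a patient lost after V3 still contributes. As shown above, this could keep power above 0.80 at 15 per arm. The reply stands in part. A reader might infer that any realistic loss leaves the trial short of its stated power, and the documents do not support a statement that broad. The offset, however, needs a V3 effect as large as the V4 effect and a correlation that is not documented. A patient lost before V3 gives no change score at all. Section 8.0 rests its 0.802 on the 6-week change and not on that model.

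Three other stronger readings are tempting and fail:

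- *Power holds only if patients complete all 18 sessions.* Session attendance is not an input to the calculation. A patient who misses sessions but walks at V4 counts in full. Missed sessions would matter only through a smaller effect or a missed final visit.
- *The protocol claims 0.802 for 16 enrolled per group.* It does not use that word. The text can be read as 16 analysable, and the defect is that it does not say which.
- *Three long outcome visits add to attrition in the arms.* V2 comes before randomisation, so stopping there does not shrink an arm. Two outcome visits follow allocation.

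It is also fair to say that the shortfall is modest. One loss per arm costs 2.8 points of power, the same as an SD of 50.4 m instead of 48.69 m, and the SD is itself borrowed from another trial.

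**Conclusion.** The concern holds as an omitted planning assumption. A reader might infer an arithmetic error, but 0.802 is correct for 16 week-6 results per arm. What is missing is the statement that those 16 must be evaluable, and what happens if they are not.

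The cost is 1.4 points of power for one patient lost overall, 2.8 for one per arm, 5.9 at 14 per arm and 9.3 at 13. These figures rest on a 50 m difference, an SD of 48.69 m, an inferred two-sided alpha of 0.05 and the single week-6 comparison in section 8.0. They say what a given loss would cost. They do not say that such a loss occurred or was likely at a particular rate.

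Nor do the documents support a claim that baseline adjustment will bring power back to 0.80. That depends on the unknown correlation and on the SD being unadjusted.

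**What to change.** No extra enrolment is proposed.

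1. In protocol section 8.0, restate the result along these lines: *16 evaluable patients per group give power 0.802 (two-sided 0.05 t-test); with 15, 14 or 13 evaluable per group it is 0.77, 0.74 or 0.71.* The sponsor should confirm the inferred alpha.
2. In the SAP's change-from-baseline mixed model for the walk test, add baseline 6-min walk distance (the better of V1 and V2, already collected) as a covariate and report the treatment effect at V4.
3. The SAP is written in the past tense and comments on how far the results of its two models agreed, so the adjusted model would be chosen after results were known. Report it as a labelled additional analysis beside the unadjusted one, and state no recovered power for it.

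The cost is one sentence, one covariate with its degree of freedom, and a slightly less favourable stated power. No new data are needed.
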